## 8.2 Statistical analyses for additional objective

### 8.2.1 Estimate Phased RFA procedure safety

Major procedure related complications include vascular complications secondary to venous access, cardiac tamponade, embolic stroke, esophageal injury, phrenic nerve injury, PV stenosis, reentrant tachycardia arrhythmias arising from ablations, mainly left Afl.

Adverse events (AE) including their relatedness to the respective procedure, are documented starting from the first documented procedure until the 12 month FU. For this analysis only adjudicated AE data (SUO form) and coded AE data (from free text fields) will be used. In addition, TIA/Stroke events will be taken from general FU forms to calculate procedure safety. Analysis will be performed at 30 days and at 12 months after procedure.

If no adverse event was documented within the 12 month FU period, the patient or the procedure is considered to be "free of AE". AEs are documented in the AE form, whereby distinctions in relatedness to which procedure (index phased RFA, repeated phased RFA or phased RFA re-ablation) will be made. Phased RFA procedure relatedness will also be taken from the AE form (Relatedness to Phased RFA procedure = related). The documented date of the AE will be used to set the point in time. For analysis purposes, phased RFA procedure safety will be calculated for first documented procedures (on procedure and patient level), separated for additional procedures (on procedure level) and for patients with additional procedures (on patient level).

Procedure safety will be calculated for procedures that have been carried out (number of RF applications per patient > 0) and disregarding procedure successfulness. This study objective will be calculated for the BAS and the FAS (Appendix B) for patients with signed eCRF.

Further analysis might be performed, e.g. procedure safety for using PVAC GOLD solely or not PVAC GOLD solely (using other catheter or using adjunctive devices).

**Table 7:** Procedure safety variables at AE form

AE due to definition	eCRF field: AE description	Related FID's annotated eCRF (V1.3, V1.4)
Vascular access complication	Vascular access complication 
 
• Hematoma or
 
• Arterio-venous fistula or
 
• Femoral artery pseudoaneurysm
 
	F31000010_6
Cardiac tamponade	Pericardial damage 
 
• Tamponade or
 
• Pericardial Effusion
 
	F31000010_8
Stroke	Stroke	F31000010_2
Esophageal injury	Atrioesophageal damage 
 
• Injury or
 
• Fistula
 
	F31000010_9
Phrenic nerve injury	Phrenic nerve damage 
 
• Injury or
 
• Palsy or
 
• Paralysis
 
	F31000010_7
PV stenosis	PV stenosis 
 
• Symptomatic or
 
• Asymptomatic
 
• % of diameter of stenosis 
 
▪ <math>\leq 50\%</math> or
 
▪ <math>>50\%</math> or
 
▪ NA
 
 
 
	F31000010_1 F31000030
Re-entrant tachycardia arrhythmias arising from ablations	Other (diagnosis) Description field	F31000010_88 F31000090
Mainly left Afl	Left Afl	F31000010_11
Other diagnostics: text complies to AEs above, text will be coded	Free text field	F31000010_88 F30000090 F30000010

**Table 8:** Procedure safety variables at FU form

AE due to definition	eCRF field: AE description	Related FID's annotated eCRF (V1.3, V1.4)
Stroke	• TIA/Stroke	F15000140 F15000150

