4.4.2 Statistical methods for additional objective

Estimate Phased RFA procedure safety

Rational: Phased RFA was shown as a safe ablation technology. Andrade, et al., reported a safety profile in the meta-analysis with a complication rate of 2.0%, including an 0.63% incidence of thromboembolic complications (20). Recently a large survey (21) on RF ablation of AF has been published. It has evaluated 2,748 patients (620 with persistent AF) from 20 European centers using the Phased RFA system. The overall complication rate was 3.9%, with a stroke and TIA incidence of 1.1%.

Twelve comparative or randomized studies have been published comparing platinum electrode catheter PVAC versus alternative conventional RF ablation catheters. Briefly, all studies demonstrated equivalent safety outcomes. The novel catheter design of the PVAC GOLD array may improve safety by reducing embolic events as it prevents electrode 1-to-10 interaction and allows for enhanced tissue contact due to the 20° forward tilt. This registry will collect information about complication rates linked to the Phased RFA system or to the procedure itself.

Major procedure related complications include vascular complications secondary to venous access, cardiac tamponade, embolic stroke, esophageal injury, phrenic nerve injury, PV stenosis, and reentrant tachycardia arrhythmias arising from ablations, mainly left Afl.

Endpoint Definition: Procedure-related and/or device-related adverse events as determined by investigator.

Analysis Methods: The number of patients with reported device and procedure related events will be summarized as a binomial variable; number and percentage of patients with events. Additionally, a Kaplan-Meier estimations will be used to summary the timing of the occurrence of safety events through 12 months. Time from onset to resolution of events may also be presented.

Measurements: Adverse events to be documented starting from the index procedure until the 12 months FU.

4.4.3 Statistical methods for ancillary objectives.

Characterize the acute procedural success rate

Rational: A cornerstone of the ablation procedure is to block electrical conduction from the PVs. According to guidelines (22) both, exit and entrance block, are equally accepted as confirmation of PVI and used as indicator of acute success.

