11.2 Vigilance Reporting

All devices used in this study are market-released. Therefore, Post Market Surveillance and product complaint reporting is applicable to all market-released devices used in the study. The reporting of product complaints abuse, and misuse of these CE-labeled devices is not part of the study and should be done in addition to the AE reporting according to regional requirements.

11.3 Adverse Events Advisory Committee (AEAC):

At regular intervals, an independent Adverse Events Advisory Committee will conduct a medical review of the AEs for adjudication. The Committee will consist of a minimum of three non-Medtronic employed physicians that are not participating investigators for the study, including the AEAC chairperson.

The AEAC is responsible for reviewing the investigator's assessment and classification of AE. The AEAC will review AEs and provide a final adjudication of relatedness and seriousness and can advise on the provided diagnosis.

For seriousness only study reportable AEs will be adjudicated. Relatedness of the AEs can be adjudicated as not related to the procedure/system or classified according to the Table 11-2.

Study lead may facilitate and participate in AEAC meetings, but will be non-voting members. The safety Medtronic personnel or study manger will provide the AEAC with the PI's description and classification AEs under review.

If the AEAC disagrees with the investigator's classification of the event, the rationale will be provided to the investigator. If the investigator agrees with the AEAC, this will be documented accordingly. If the investigator does not agree with the AEAC classification, both determinations will be documented within the study report. However, the AEAC determination will be used for analysis purposes.

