### 7.2.4 Adverse Event data

Adverse event data (from AE form) will be listed, ordered and reported by seriousness and relatedness to the procedure. Further adverse event analysis are described in the additional objective of this study (SAP chapter 8 and 8.2). For Adverse event analysis only AEAC adjudicated (SUO form) events will be analysed.

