## 8.2.2 Methodology for analysing the procedure safety

The number of patients with reported device and procedure related events will be summarized as a binomial variables for each event and combined; number and percentage of events and patients with events (up to 12 month after first documented procedure). Additionally, Kaplan-Meier estimations (time-to-first-event analysis) will be used to summary the timing of the occurrence of safety events through 30 days and 12 months (351 days) after first documented procedure. Time from onset to resolution of events will also be presented. Further strata may be applied for analysis (e.g. reason for ablation: index, repeated, re-ablation, left Afl).

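### SAP 8.2.1 adds TIA/stroke from general follow-up forms to procedure safety without adjudication, a relatedness source or matching to AE forms, in conflict with the related-event endpoint

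*SAP*

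**What the plan says.** Protocol 4.4.2 defines the safety endpoint as adverse events related to the procedure or the device, as judged by the investigator. Protocol 11.3 has the AEAC review that judgement and says that, if the two disagree, "the AEAC determination will be used for analysis purposes". SAP 7.2.4 follows this: "For Adverse event analysis only AEAC adjudicated (SUO form) events will be analysed".

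SAP 8.2.1 opens in the same way: "For this analysis only adjudicated AE data (SUO form) and coded AE data (from free text fields) will be used". Its next sentence adds a second source: "In addition, TIA/Stroke events will be taken from general FU forms to calculate procedure safety". On relatedness it says: "Phased RFA procedure relatedness will also be taken from the AE form (Relatedness to Phased RFA procedure = related"). On timing: "Analysis will be performed at 30 days and at 12 months after procedure".

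Table 7 lists the AE-form variables. Table 8 lists the follow-up-form variables and has a single row, TIA/Stroke, with fields F15000140 and F15000150.

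SAP 8.2.2 describes the binomial summary as covering events related to the device and procedure, reported both as events and as patients. Kaplan-Meier estimates run "through 30 days and 12 months (351 days) after first documented procedure".

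**The concern.** The endpoint is a rate of related events. The added source brings in events for which the SAP gives no way to establish relatedness. A rate built from both sources would be neither a related rate nor a reliable all-cause rate, because general follow-up visits are unscheduled and follow each site's routine.

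The events at issue are few and important. The protocol's safety rationale cites a survey of this system: "The overall complication rate was 3.9%, with a stroke and TIA incidence of 1.1" per cent. At 1.1%, 800 patients would yield 8.8 events, so even two or three added events would be visible. Two programmers working from 8.2.1 and 8.2.2 could also produce different safety tables from the same data.

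**Working it through.** The plan states no figure for this analysis, so there is none to reproduce. The check has two parts: a comparison of the texts, then an illustration of size.

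**Comparison of the texts**

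- *Adjudication.* SAP 7.2.4 and Protocol 11.3 require it. SAP 8.2.1 attaches no such condition to follow-up-form events, and no section routes them to the AEAC.
- *Relatedness.* Protocol 4.4.2 and SAP 8.2.2 require it. The only source named in SAP 8.2.1 is the AE form, and Table 8 names no relatedness variable.
- *Matching.* No rule links a follow-up-form stroke to an AE form for the same event. SAP 8.2.2 reports the number of events as well as the number of patients, so a duplicate would inflate the event count. It would not change the percentage of patients or the time-to-first-event estimates.
- *Which events are added.* Protocol 11 collects procedure- and system-related AEs, and 11.1 says that reporting all serious AEs is outside the registry. Protocol 7.2 requires an AE form when a general follow-up visit is due to a related AE. A related stroke should therefore already have an AE form. Events found only on a follow-up form would be mainly those the site did not judge related, plus related ones whose AE form was missed.
- *TIA.* Table 7 takes Stroke (F31000010_2) from the AE form and has no TIA row. Table 11, for the anticoagulation objective, uses F31000010_2 and F31000010_3 for TIA/stroke. Within the safety objective, TIA is named explicitly only through the unadjudicated source.

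**Illustration of size**

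Inputs:
- r, the related stroke/TIA rate: 1.1% (survey) or 0.63% (thromboembolic complications in the meta-analysis), both from Protocol 4.4.2.
- u, the annual rate of unrelated stroke/TIA: not in the documents; assumed 0.25% to 2%.
- Horizons: 351 days and 30 days (SAP 8.2.2).
- N: 800 and 1000 (SAP 3.3).

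Rate at 12 months if every unrelated event is captured and counted: r + (1 − r) × u × 351/365.25, where 351/365.25 = 0.961.

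For r = 1.1%:
- u = 0.25%: 0.011 + 0.989 × 0.0025 × 0.961 = 1.34%
- u = 2%: 0.011 + 0.989 × 0.02 × 0.961 = 3.00%

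Added events = N × u × 0.961.

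| Assumed u per year | From 1.1% | From 0.63% | Added events, N = 800 | Added events, N = 1000 |
|---|---|---|---|---|
| 0.25% | 1.34% | 0.87% | 1.9 | 2.4 |
| 0.5% | 1.58% | 1.11% | 3.8 | 4.8 |
| 1% | 2.05% | 1.58% | 7.7 | 9.6 |
| 2% | 3.00% | 2.54% | 15.4 | 19.2 |

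The same formula applied to the survey's overall complication rate of 3.9% gives 4.13% to 5.75%.

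At 30 days the addition is (1 − r) × u × 30/365.25. For r = 1.1% this is 0.989 × 0.0025 × 0.0821 = 0.02 percentage points, up to 0.989 × 0.02 × 0.0821 = 0.16 percentage points.

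**The case against.** The strongest reply is that SAP 8.2.2, the methods section for this objective, speaks of related events and so already filters out the rest. That wording does stand, and it rules out saying that unrelated strokes will certainly be counted. It does not settle the matter. No relatedness source is named for a follow-up-form stroke, and a filter that relies on the AE form would largely cancel the addition made in 8.2.1. The two sections still have to be reconciled.

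Other points carry weight:

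- SAP 7.2.4 begins by referring to AE-form data, so its adjudicated-only rule can be read as governing that form alone, with 8.2.1 as a deliberate addition. This softens the conflict with 7.2.4 but leaves the one with Protocol 4.4.2, whose endpoint is related events.
- The annotated eCRF is not in the text available, so what F15000140 and F15000150 record cannot be checked. The SAP itself names no relatedness field.
- Read literally, 8.2.1 covers general follow-up forms only, so events first reported at the 12-month visit or call might not enter. The illustrated figures are therefore upper ones.
- Protocol 4.4.3 plans Kaplan-Meier rates of procedure-related TIA/stroke in the first three days, and SAP 8.3.3 (Table 11) draws related TIA/stroke from the procedure and AE forms. That analysis does not use follow-up forms, so a related figure will exist whatever 8.2.1 does.
- Searching follow-up forms is sensible as a way to find missed AE forms. That is a reason to adjudicate what is found, not to count it all.

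**Conclusion.** The gap is real: follow-up-form TIA/stroke enters procedure safety without adjudication, a relatedness source or matching, and this conflicts with the endpoint as defined elsewhere in both documents. Followed literally, the 12-month rate can include events not judged related, and the event count can include duplicates.

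A reader might go further and infer that unrelated strokes will be counted and that the reported rate will be two to three times too high. The documents do not support that. SAP 8.2.2 still describes related events, and no background rate is given. The range of about 1.3% to 3.0% at 12 months, from a related rate of 1.1%, rests on four assumptions: u between 0.25% and 2% per year, full capture on follow-up forms, no filtering under 8.2.2, and 1.1% standing for the related rate at 12 months. The protocol gives neither a time horizon nor an attribution rule for that 1.1%. The effect at 30 days is small, and the separate analysis of related TIA/stroke is untouched.

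**What to change.** Amend SAP 8.2.1, Table 8 and SAP 8.2.2 to state that:

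1. each TIA/stroke on a follow-up form is matched to AE forms by patient and date, and a matched event is counted once;
2. each unmatched event goes to the AEAC, which under Protocol 11.3 can already classify an event as not related;
3. an unmatched event counts in procedure safety only if adjudicated as related;
4. all TIA/stroke from any form is reported on a separate line.

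The same edit should say whether TIA belongs to the procedure safety endpoint and, if so, add its AE-form field to Table 7.

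The cost is SAP wording, some extra cases for an existing committee, and site queries, because the AEAC works from the investigator's description and classification. Under the assumed range, unrelated events would add about 2 (N = 800, 0.25% per year) to 19 cases (N = 1000, 2% per year), plus any related events whose AE form was missed.

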Unsuccessfulness per vein is considered, if the vein is not isolated or not verified. Percentages for success will be shown per vein for patients treated with PVAC GOLD, all PVs were isolated at the end of the procedure = no and all PVs isolated by using PVAC only = no.

**Table 9:** Procedure success variables from Procedure and AE form

Objective section	Definition (used variables)	Related FID's annotated eCRF (V1.3, V1.4)
Procedure attempt was not declined due to technical issues related to Phased RFA system	Procedure form: Date of procedure Phased RFA procedure successful?  No – Due to AE AE form: Date of AE Was the event related to technical issues?* Related/Possibly related	F20000010 F22000180 F22000190  F30000010 F30000070
Only PVAC catheter(s) used to achieve PVI	Procedure form: Phased RFA catheters used PVAC GOLD (solely) Number of RF applications per patient > 0  Were all PVs isolated at the end of the procedure Were all PVs isolated by using only PVAC	eCRF V1.3/V1.4 F21000010  F20001000 eCRF V1.4 only F22000062  F22000066

All accessible PVs were isolated (entrance and/or exit block confirmation per vein)	Were all accessible PVs isolated at the end of the procedure entrance block and/or exit block Exit block and/or Entrance block	eCRFV1.3/V1.4 F22000010 F22000020 F22000030 F22000040 F22000050 F22000060
---	--	---

\* Precondition: If the documented AE is related to technical issues with Phased RFA system components, the date of the latest procedure must be  $\leq$  date of the AE. For patients with more  $> 1$  procedure, the latest procedure will be the related procedure.

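### The SAP's safety endpoint does not match the protocol's: no rule says whose relatedness judgement counts, AE-form TIAs and unlisted related events have no defined place, and effusion is pooled with tamponade

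*SAP*

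**What the plan says.** **Relatedness.** Protocol 4.4.2 gives "Endpoint Definition: Procedure-related and/or device-related adverse events as determined by investigator". Protocol 11.3 has the AEAC give the final adjudication of relatedness and seriousness. If the investigator still disagrees, both views are documented. "However, the AEAC determination will be used for analysis purposes".

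SAP 7.2.4 states "For Adverse event analysis only AEAC adjudicated (SUO form) events will be analysed". SAP 8.2.1 says much the same and adds coded free text: "For this analysis only adjudicated AE data (SUO form) and coded AE data (from free text fields) will be used". The next paragraph of 8.2.1 then says "Phased RFA procedure relatedness will also be taken from the AE form (Relatedness to Phased RFA procedure = related".

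**Content.** SAP Table 7 lists the AE-form safety variables as named diagnoses. Its last row admits free text on this condition: "Other diagnostics: text complies to AEs above, text will be coded". The stroke row carries only code F31000010_2. Table 8 adds TIA/stroke from the follow-up form. Table 11 (SAP 8.3.3) uses F31000010_2 and F31000010_3 for TIA/stroke. The *Cardiac tamponade* row is filled by either tamponade or pericardial effusion, under one field. SAP 8.2.2 promises counts of device- and procedure-related events, singly and combined. SAP 7.2.4 adds that AE-form data "will be listed, ordered and reported by seriousness and relatedness to the procedure".

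**The concern.** Safety is the registry's only additional objective. Its rate will be read beside the survey figures in the protocol's rationale: 3.9% complications overall and 1.1% stroke and TIA. Two programmers following the SAP could produce different rates, because the source of relatedness, the scope of the combined count and the TIA source are each left open or inconsistent. One natural reading of 8.2.1 also breaks protocol 11.3 and gives the treating operator the decision that the AEAC was set up to make. Where the SAP departs from the protocol's main endpoint it says so (8.1.1). It gives no such notice for safety, although protocol 4.4 requires changes in method to be described and justified in the SAP.

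**Working it through.** The documents give no sample size or precision for safety, so there is no planned figure to reproduce. The check is a comparison of texts, followed by an illustration of size.

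**1. Whose relatedness counts.** For an event already adjudicated:

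| AEAC | AE-form procedure item | Protocol 11.3 | AE form governs | Both needed | Either suffices |
|---|---|---|---|---|---|
| related | related | counts | counts | counts | counts |
| not related | related | no | counts | no | counts |
| related | not related | counts | no | no | counts |

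The word *also* in 8.2.1 fits any of the last three columns. None of them agrees with protocol 11.3 in both discordant rows.

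**2. Direction.** Protocol 11 collects only procedure- and system-related AEs. An event the investigator thinks unrelated would normally never reach the AEAC. The second row is therefore the likelier conflict: an event the AEAC judged unrelated is kept. The third row remains possible, for example when an event is reported as system-related only and the AEAC classes it as procedure-related.

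**3. TIA.**

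| Where recorded | In safety variables? | Relatedness or adjudication check stated? |
|---|---|---|
| AE form, stroke (F31000010_2) | yes, Table 7 | yes, but in conflict (step 1) |
| AE form, F31000010_3 | no | not applicable |
| Follow-up form, TIA/stroke | yes, Table 8 | no |

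That F31000010_3 is TIA is inferred from Table 11. Protocol 7.2 has AEs checked during the procedure and at discharge, before any follow-up visit. A peri-procedural TIA may therefore be recorded only on the AE form and be missed, while a late unrelated TIA on a follow-up form may be counted.

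**4. Scope.** The protocol endpoint is all related AEs. Table 7 has no row for a related event outside its list. It has none for a related death, which protocol 11.1.1 requires on an AE form. SAP 8.2.1 names a procedure-relatedness item but no device item, although 8.2.2 needs one.

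**5. Tamponade.** The row has no severity condition, so any effusion reported as an AE falls under the tamponade label.

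**6. Size, illustration only.** Inputs are 3.9% and 1.1% (protocol 4.4.2) and n = 1000 (protocol 4.3). The split of the 1.1% between stroke and TIA is not given.

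- Overall: 1000 × 0.039 = 39 patients (exact 95% CI 2.8% to 5.3%). Stroke and TIA: 1000 × 0.011 = 11.
- If all 11 were TIAs and all were missed: (39 − 11)/1000 = 2.8% (CI 1.9% to 4.0%). If half were TIAs: (39 − 5.5)/1000 = 3.35%. If none: 3.9%.
- At n = 800: 31 − 9 = 22 patients, so 3.9% falls to about 2.8%.
- If 10%, 20% or 30% of related events lay outside Table 7 (assumed) and were not counted: 39 × 0.9, 0.8 or 0.7, giving about 3.5%, 3.1% or 2.7%.
- In the other direction, each patient counted only because of an event the AEAC judged unrelated adds 1/1000 = 0.1 percentage points.

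The documents give nothing from which to estimate the rate of disagreement or the number of effusions.

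**The case against.** The strongest reply is that the SAP twice confines AE analysis to adjudicated events, that the contested sentence says *also*, and that it follows a sentence about which procedure an event belongs to. Appendix B places an AEAC chapter within the AE segment, and the annotated eCRF is not available. This stands to the extent that 8.2.1 is an unresolved conflict, not plain reliance on the investigator. It does not remove the conflict: SAP 6.2 calls the AE form the SUE form, while adjudicated data come from the SUO form, and protocol 4.4.2 itself names the investigator.

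A reader might infer more than the documents support:

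- *TIAs are lost.* Not as such. Table 8 brings in those on follow-up forms, and Table 11 reports AE-form TIA/stroke under the anticoagulation objective. The gap is a TIA recorded only on the AE form.
- *The filter drops possibly related events.* The level "Related/Possibly related" in Table 9 belongs to the technical-issues question. Nothing shows that the procedure item has it.
- *Device-only events are excluded.* SAP 8.2.2 includes them; 8.2.1 only fails to name the field.
- *Unlisted events vanish.* They would appear in the 7.2.4 listings, and 8.2.1 calls a patient free of AE only if none was documented. A listing is still not the endpoint rate.
- *The tamponade rate will be overstated.* Table 7 shows the two options separately and SAP chapter 8 promises counts by category, so this is a labelling fault that may or may not reach the report. Effusion belongs in an all-related endpoint; it does not belong under the name tamponade.

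It is also true that safety is exploratory, with no hypothesis or threshold, and that no formal comparison with the survey is planned. That limits the consequences. It does not excuse an endpoint that differs from the protocol's.

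**Conclusion.** The point holds in four parts. The relatedness source contradicts protocol 11.3 or is left open, and the protocol contradicts itself. AE-form TIA is missing from the safety variables, while follow-up-form TIA/stroke enters without a stated check. Table 7 is narrower than the protocol endpoint and 8.2.1 names no device-relatedness field. Effusion is pooled under a tamponade label.

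The net bias is of unknown sign: relatedness conflicts more likely raise the rate, while the TIA and scope gaps lower it. The fall from 3.9% to 2.8% bounds the TIA gap only. It assumes that the survey rates apply here, that every stroke/TIA event is a TIA affecting a separate patient with no other counted event, and that follow-up forms recover none. The reading of F31000010_3 as TIA needs confirmation on the annotated eCRF.

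**What to change.** In SAP 8.2.1:

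- State that AEAC-adjudicated procedure and system relatedness defines the endpoint, with the investigator's assessment as a sensitivity analysis.
- Define the combined endpoint as all AEs the AEAC classes as procedure- and/or system-related, including related deaths, with Table 7 as named sub-categories.
- Add F31000010_3 to Table 7 once the annotated eCRF confirms that it is TIA.
- Apply the same relatedness rule to TIA/stroke taken from follow-up forms.
- Report tamponade and pericardial effusion on separate lines.

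In the protocol, align 4.4.2 with 11.3.

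The main cost is SAP wording and programming on AE and adjudication data already planned, plus the protocol alignment. Follow-up-form TIA/stroke events without an AEAC decision would need one. The reported rate may move in either direction.
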